**Requested Waivers/Alterations of Consent:**

Waiver of Informed Consent	Request for waiver of consent for providers and staff to be exposed to EHR-based intervention facilitating lung cancer shared decision making for patients meeting USPSTF eligibility criteria for this clinical service
Waiver of Informed Consent	Request for waiver of consent for patient to have their providers and staff to have access to the IT intervention promoting standard of care, and to evaluate their data to assess intervention impact.

**Procedures:**

Listed below are the procedures for the human subjects research aspects of this project. Procedures for activities outside of humans subjects research are not listed, such as engagement with standards development organizations to advance relevant health IT standards; software development, implementation and monitoring undertaken to fulfill clinical operations and operational QI responsibilities rather than for research purposes; and making the software developed in this project available in EHR app stores.

## **Aim 1. System Design and Development**

*Pre-Implementation Provider and Staff Interviews:* During each interview, the interviewer will ask the participant to recall a recent relevant patient and provide a 1) summary, 2) timeline, and 3) a deepened description. After each interview, we will display the intervention or a mock-up (if not yet fully implemented) and conduct usability assessments. The interviews will be coded and modeled through consensus by members of the research team. The results of the interviews will be used to guide refinement of the intervention. Interviews are expected to take approximately 45 minutes to 1 hour, taking place outside of normal work hours. Audio and screen recordings will be made of the interviews where appropriate with participant consent. Screen recording tools may include eye tracking. We may record the screen, eye movements, and audio to analyze the app use by the participant. Audio-recordings may be transcribed.

## **Aim 2. Implementation**

*Provider and Staff Participation in Pilot Implementation:* To account for real-world conditions, the interventions will be pilot tested by providers and staff who volunteer to serve as pilot users or provide care related to lung cancer screening for the targeted patient population at a pilot clinic.

*Patient Participation in Pilot Implementation:* Patients will be included in the pilot implementation if they meet the pilot implementation inclusion criteria as described earlier.

*Provider and Staff Participation in Clinical Trial:* The project team will work with leaders in primary care at the University of Utah to identify how best to incorporate the intervention into clinical workflows. Based on these discussions and following assent by the clinical leaders, we anticipate that we will visit each clinic to describe the intervention, conduct training, and answer questions. It is anticipated that usual clinical staff meetings will be leveraged for this purpose. Providers and designated staff will have access to the intervention in the EHR. Providers and staff will be free to follow or disregard the intervention's suggestions as they see fit.

There will not be randomization in this study. The intervention will be rolled out systemwide.

The intervention will consist of the following core items:

- An EHR-integrated shared decision making (SDM) tool for providing information on the risks and benefits of lung cancer screening through low-dose computed tomography (LDCT) testing. An initial version of this tool (Decision Precision+) was previously approved for operational clinical use outside of this research study. A current version of the standalone version of the SDM tool is available at <https://share.lungdecisionprecision.com/>.
- Reminders in the EHR to offer SDM for LDCT for patients eligible for lung cancer screening according to USPSTF guidelines. Epic "Health Maintenance" reminders for this purpose were also previously approved for operational clinical care through usual clinical governance channels. Additional reminders may be provided using other EHR-based mechanisms, including through an Epic-integrated disease management and health maintenance system that is also already available in the Epic EHR system at the University of Utah.

Based on feedback received from users, it is anticipated that at least one cycle of improvement will be released into the intervention during the course of the pragmatic implementation trial. For study power analysis purposes, we anticipate one improvement release approximately 9 months into the trial, with the trial anticipated to last 18 months. We anticipate the intervention will remain as a part of routine clinical care following the trial. In addition to these major enhancements, less significant updates or bug fixes, if any, will be released as clinically required. All major enhancements will be introduced with the support and approval of the appropriate governance group, such as the Community Physicians Group Medical Directors or the EHR Operations committee. While the nature of the major intervention enhancements will be dependent on user feedback, we currently anticipate that one or more of the following will be introduced as the enhancements:

- Providing eligible patients with the recommendation to undergo shared decision making for lung cancer screening. This is already done for many USPSTF recommended preventive care reminders. We anticipate that we will provide these care reminders through the Epic MyChart personal health record portal.
- Introducing Epic Health Maintenance prompts for medical assistants to collect detailed smoking history for patients who may be eligible for screening (age 55 to 80 with a history of smoking and no lung cancer diagnosis) but who lack the detailed smoking history data required to make a complete determination (e.g., pack-years of smoking and years since quit smoking).
- Facilitating patient education outside of the clinic visit, e.g., through printing out the shared decision making materials during the visit, for patient review prior to a follow-up discussion with the provider at a subsequent visit.

Following the roll-out, clinic leaders may receive periodic feedback on use of the intervention and LDCT screening rates, including comparisons to other clinics. Clinic leaders may be given user-level data so that outlier performances can be addressed if desired. Activities for facilitating implementation may include regular email, phone, or in-person communication with clinic leaders to discuss CDS adoption and address barriers to adoption; identify “implementation pearls”; and share these “pearls” with other clinics. We and others have shown that such facilitation activities improve the adoption and impact of practice change interventions. Contact frequency will be determined by workflow adoption, with more intensive follow-up directed to clinics with lower adoption rates. We will maintain a log of interactions to identify common issues, and issues will be prioritized and addressed.

*Patient Participation in Clinical Trial:* Patients will be included in the clinical trial if they meet the clinical trial inclusion criteria described earlier.

*Post-Implementation Provider and Staff Interviews:* Early formative interviews will be conducted with care team members at the pilot clinic, and potentially other intervention clinics, as the users respond to the intervention. The purpose is to examine impact on workflow, uncover any usability problems, refine implementation procedures, and identify any training needs. Interviews are expected to take approximately 45 minutes to 1 hour. Audio and screen recordings will be made of the interviews where appropriate with participant consent. Audio-recordings may be transcribed. Screen recording tools may include eye tracking. Some screen captures may include actual patient data. We may record the screen, eye movements, and audio to analyze intervention use by the participant for later analysis or for participants to comment on their thought process as they review their own recordings.

### **Aim 3. Evaluation**

*Patient Outcomes Assessment:* Data for analysis will be extracted from the University of Utah data warehouse and system logs. Outcome measures are described under section 9 below. A PhD-level statistician co-investigator will oversee the statistical analyses. Patients for whom the intervention was used prior to the clinical trial will be excluded from the main clinical trial analyses.

*Provider and Staff App Usage Assessment:* The same approach as for the Patient Outcomes Assessment will be used.

*Provider and Staff Surveys:* Providers and staff will be surveyed regarding their satisfaction with the intervention using the System Usability Scale (SUS), with supplemental questions on barriers and facilitators to usage as well as questions on the impact on workflow and

workload. We will also ask whether respondents are interested in the focus groups described next. Providers and staff will be surveyed electronically, with invitations sent via email.

*Patient Surveys:* Patients will be surveyed electronically and/or on paper with invitations, surveys, and pre-paid return envelopes sent by mail. Patients will be surveyed regarding their screening preferences, knowledge, preference for SDM, decisional conflict, and satisfaction with provider communication. We will also ask whether respondents are interested in the focus groups described next.

*Provider and Staff Focus Groups:* The focus groups will evaluate the intervention specifically, as well as explore the implementation and adoption issues with CDS, SDM, and guideline-focused care in general. Methods suggested by Krueger and associates will be utilized, including a prepared script (Introduction, Overview, Ground Rules, and Questions), use of non-threatening group processes, and homogenous groups. We will focus on facilitators and barriers to CDS adoption. Each focus group is expected to take 1-1.5 hours. Discussions will be recorded and may be transcribed.

*Patient Focus Groups:* The same methods as for the Provider and Staff Focus Groups will be used.

*Stakeholder Interviews:* We will interview key stakeholders at each of the implementation sites, including dissemination sites in other healthcare systems, with a goal of understanding barriers and facilitators to the scalable dissemination of evidence-based CDS, as well as to estimate the associated time and resource costs. To facilitate cost estimation, stakeholders will be asked to keep track of significant resource expenditures.

*Data Quality Assurance:* Because the intervention is promoting standard of care, we will base our approach on how University of Utah Health operationally introduces other health IT interventions to promote standard of care. As part of standard quality assurance procedures, we will assess all adults who had an outpatient visit in University of Utah Health primary care. Data for smokers would be analyzed to find inaccuracies and new estimates for lung cancer risk and eligibility for lung cancer will be produced.

Our grant application matches the ERICA application in the following areas: study design, study population, study objectives and goals, and study test interventions and procedures. Surveys, interview guides, and focus group guides have been uploaded in the Document and

Attachment section. In case of any edits, all of these materials will be submitted to the IRB via amendment for review and approval before they are used with participants.

**Procedures performed for research purposes only:**

## **Statistical Methods, Data Analysis and Interpretation**

---

### **Aim 1. Design**

*Pre-Intervention Provider and Staff Interviews:* Records will be analyzed using qualitative analysis software (such as ATLAS or NVivo), which can integrate transcripts, pictures, memos and other materials. We will use procedures recommended by Patton and others that focus on developing coding protocols to highlight issues, problems, and potential recommendations.

### **Aim 2. Implementation**

*Pilot Implementation and Clinical Trial:* see below for analyses for the pilot implementation and clinical trial.

*Post-Implementation Provider and Staff Interviews:* The purpose is to examine impact on workflow, uncover any usability problems, refine implementation procedures, and identify any training needs. We will use qualitative analyses procedures similar to Aim 1.

### **Aim 3. Evaluation**

*Patient Outcomes Assessment:* The primary outcome is the proportion of patients eligible for LDCT screening per USPSTF guidelines receiving LDCT screening. Planned secondary outcomes are the expected number of lung cancer deaths prevented given the risk profiles of individuals screened with LDCT, the expected number of major complications given the risk profiles of individuals screened with LDCT, and, if approved by the University of Utah Value Driven Outcomes research committee, the operating margin attributable to study patients during study period (total revenues minus total cost). Data for the operating margin analysis

will leverage the Value Driven Outcomes value analysis tool co-developed by PI [name] to determine the true costs of care.

We will report the number of patients and patient characteristics for each phase of the interrupted time series (ITS) study. We anticipate a 12-month baseline phase, a 9-month intervention phase, and a 9-month enhanced intervention phase which incorporates improvements made to the CDS intervention based on initial experience. We will conduct a segmented regression analysis to fit the monthly series and assess the extent to which the intervention was associated with changes in outcome measures. The study phases constitute three segments of regression models with monthly time points. We will use the segmented least squares approach with parameters for intercept, baseline trend, and changes in the level and trend after the intervention. We will start with assuming a linear trend line within each segment. Nonlinearity trends will be explored if the linear assumption is violated. We will use the Durbin Watson statistic as a measure of autocorrelation and test up to six-order autocorrelation. Potential confounding is limited to covariates associated with the outcome that change at the time of the intervention. We will test for confounding due to changes in study population characteristics such as age, gender and race. Statistical significance will be defined at alpha = 0.05.

To mitigate the impact of pandemic COVID19, we will make the following two modifications in the statistical analysis plan. First, we will redefine the baseline phase so that it has no overlap with the lockdown period, because all the non-essential medical visits have been cancelled during this period. Secondly, we anticipate the patient characteristics and composition during the intervention phase and even enhanced intervention phase might be different from the baseline phase which is observed before the pandemic. We will compare the distributions of patient characteristics across the three phases of the ITS study. If significant discrepancies are observed in the patient characteristics and composition, we will conduct propensity score modeling and use a matching or weighting approach to create a comparable study cohort in each phase before running the originally proposed segmented regression analysis. If any lock-down periods coincide with the intervention phases, we may remove visits occurring during these periods from the analysis.

To estimate statistical power, we followed Rozario, Moore and McWilliams' approach, and used the statistical software SAS. We assumed the proportion of eligible patients receiving LDCT screening, the primary outcome in the study, will increase from the current 6.4% to at least 12.8% during the intervention phase and 20% during the enhanced intervention phase. Empirical EHR data indicate at least 900 patients per month will meet USPSTF LDCT eligibility criteria throughout the study period. With this conservative monthly sample estimation and the length of time at each phase, we would have more than 95% power to detect

the hypothesized differences in the primary outcomes at different phases. All the estimated statistical powers were calculated based on two-sided tests with a significance level of alpha = 0.05.

*Provider and Staff App Usage Assessment:* Utilization metrics will include the number of clinics, providers, and other empowered staff utilizing the intervention.

*Provider and Staff Surveys:* Descriptive data analysis will be conducted and aggregated data will be compared across groups.

*Patient Surveys:* The same methods will be used as for the provider and staff surveys.

*Provider and Staff Focus Groups:* Records will be analyzed using qualitative analysis software (such as ATLAS or NVivo) which can integrate transcripts, pictures, memos and other materials. We will use procedures recommended by Patton and others that focus on developing coding protocols to highlight issues, problems, and potential recommendations.

*Patient Focus Groups:* The same methods will be used as for the provider and staff focus groups.

*Stakeholder Interviews:* The same methods will be used as for the provider and staff focus groups.

*Data Quality Assurance:* Data for smokers would be analyzed to find inaccuracies and new estimates for lung cancer risk and eligibility for lung cancer will be produced. We will use smoking history data entered in the EHR in the designated structured fields. Detailed smoking history could be recorded in 5 fields: smoking status, packs per day, years smoked, smoking start date and smoking quit date. In our system, which uses the default EHR configuration for smoking history documentation, smoking start date is usually missing as it can only be entered by patients through the patient portal. More granular smoking status data will be classified into current and former smoker categories. We will aim to develop an algorithm which could be

used in the future to more accurately predict eligibility for lung cancer screening. Intermediary evaluation measures for this algorithm will include whether patients have sufficient data to calculate eligibility, pack-years and years since quit on 2021/01/01.

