## Background and Introduction

---

Lung cancer is prevalent and deadly. Lung cancer is the second most commonly diagnosed cancer in the United States (US), with an estimated 234,030 new diagnoses in 2018, and it is the leading cause of cancer-related deaths among both men and women, with an estimated 150,050 deaths in 2018. Lung cancer accounts for approximately 1 in 4 cancer-related deaths. The primary risk factor for lung cancer is cigarette smoking.

Low-dose computed tomography (LDCT) screening is effective for reducing lung cancer mortality. The National Lung Screening Trial (NLST) enrolled 53,454 participants aged 55 to 74 years who had a history of cigarette smoking of at least 30 pack-years and, if former smokers, had quit within the past 15 years. This study randomized participants to screening with either LDCT or chest radiography. Compared to the radiography group, LDCT resulted in a 20% relative reduction in lung cancer mortality ( $p = 0.004$ ). This 20% relative reduction in lung cancer deaths with screening is larger than the reduction in breast cancer deaths with mammograms. Based on this finding, the US Preventive Services Task Force (USPSTF) recommended in 2013 that annual LDCT be performed for lung cancer screening in patients meeting NLST enrollment criteria. The USPSTF recommendations expand the eligible age range from 55 to 80 years inclusive. The US Preventive Services Task Force (USPSTF) provided a grade B recommendation in 2013 that annual LDCT lung cancer screening be offered to patients 55 to 80 years old with a 30+ pack-year smoking history who are current smokers or quit in the last 15 years. In March 2021, the USPSTF updated its recommendation to lower the eligibility age to 50 and the smoking requirement to 20+ pack-years. The revised criteria should reduce lung cancer mortality by an additional 33% while increasing the number of screening-eligible patients by 67%.

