LDCT can result in significant harm, with the balance of benefits and harms dependent on the patient's risk profile. The NLST found substantial harms associated with LDCT screening, including high false positive rates (96.4%) which can lead to unnecessary and potentially harmful invasive procedures. Moreover, additional studies found that the balance of benefits and harms is highly dependent on the patient's risk profile. These studies developed validated models for predicting the likelihood of lung cancer, false positive LDCT tests, and adverse events based on patient-specific risk factors including age, gender, smoking history, and asbestos exposure. Among LDCT-eligible patients, the ratio of false positive results to LDCT-prevented lung cancer death range from 1,648 among those in the lowest quintile of risk to 65 for those in the highest quintile of risk.

Shared decision making (SDM) ensures that patients and providers make informed, patient-centered decisions regarding LDCT screening. Because the net benefit of LDCT screening can

vary dramatically across eligible patients, the USPSTF strongly advocates for SDM, asserting that “the decision to begin screening should be the result of a thorough discussion of the possible benefits, limitations, and known and uncertain harms.” In a 2015 decision memo, the Centers for Medicare and Medicaid Services (CMS) required a SDM consultation involving use of a decision aid for payment of initial LDCT screening. SDM is the process wherein the provider shares medical information about options and patients share their values and preferences. Following the sharing of information by both parties, the patient and provider collaborates to decide on the course of action that reflects both the best medical evidence and the patient’s preferences and values.

Current LDCT screening rates among eligible patients is <5% nationally. Despite the USPSTF recommending LDCT in 2013, the percentage of eligible smokers who received LDCT screening in the past 12 months remained low and constant, from 3.3% in 2010 to 3.9% in 2015, and a more recent analysis found no improvements. At University of Utah Health, 6.4% of eligible patients received LDCT screening in year preceding August 2018.

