## Purpose and Objectives

---

The purpose of this project is to increase appropriate low-dose computed tomography (LDCT) lung cancer screening through the development and wide dissemination of patient-centered clinical decision support (CDS) tools that (1) are integrated with the electronic health record (EHR) and clinical workflows, (2) prompt for shared decision making (SDM) when patients meet screening criteria, and (3) enable effective SDM using individually-tailored information on the potential benefits and harms of screening. The study will promote standard of care that is endorsed by the Centers for Medicare & Medicaid Services (CMS) and the US Preventive Services Task Force (USPSTF). The US Preventive Services Task Force (USPSTF) provided a grade B recommendation in 2013 that annual LDCT lung cancer screening be offered to patients 55 to 80 years old with a 30+ pack-year smoking history who are current smokers or quit in the last 15 years. In March 2021, the USPSTF updated its recommendation to lower the eligibility age to 50 and the smoking requirement to 20+ pack-years.

This project is supported both operationally and by an Agency for Healthcare Research and Quality (AHRQ) R18 grant.

The EHR-based CDS tools are being developed by the University of Utah ReImagine EHR team, directed by [name]. Within University of Utah Health, [name] is also Associate Chief Medical Information Officer and Director of the health system's Knowledge Management and Mobilization unit. [name] team receives operational funding from University of Utah Health to develop EHR-based solutions to improve patient care and the provider experience. Grant funding such as the current AHRQ R18 grant enable this operational team to allocate more resources to the optimal design, development, and implementation of these software tools, as well as to undertake more rigorous intervention design and evaluation procedures that would not be possible in the context of operational quality improvement (QI).

This project will leverage Decision Precision (<https://share.lungdecisionprecision.com/>), a validated Web-based tool for LDCT SDM developed at the Veterans Health Administration, as well as an initial version of Decision Precision+, an EHR-integrated version of the tool which can be accessed directly in the EHR and auto-populate relevant patient data in the tool instead

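### The primary proportion does not separate first from annual repeat LDCT and has no counting window or re-entry rule, so launch-cohort repeats could be read as an enhancement trend

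*Combined protocol and SAP*

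**What the plan says.** Statistical Methods, Aim 3. Evaluation: "The primary outcome is the proportion of patients eligible for LDCT screening per USPSTF guidelines receiving LDCT screening". The section does not distinguish first from repeat scans, has no rule on being due, sets no window over which a scan is counted, and does not say whether a patient may enter more than one month.

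The design is a monthly interrupted time series: "We anticipate a 12-month baseline phase, a 9-month intervention phase, and a 9-month enhanced intervention phase". Study Procedures, Aim 2 adds that "we anticipate one improvement release approximately 9 months into the trial, with the trial anticipated to last 18 months". The model is segmented least squares with level and trend changes over three segments. The power paragraph assumes that the proportion "will increase from the current 6.4% to at least 12.8% during the intervention phase and 20% during the enhanced intervention phase".

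Screening is described as annual. Purpose and Objectives cites the recommendation that "annual LDCT lung cancer screening be offered to patients 55 to 80 years old". The 6.4% is a 12-month look-back figure (Background and Introduction): "At University of Utah Health, 6.4% of eligible patients received LDCT screening in year preceding August 2018".

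The only exclusion for prior exposure (Study Procedures, Aim 3) covers patients for whom the tool was used before the trial.

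**The concern.** A patient who accepts a first scan normally stays eligible and is due again a year later. The launch is expected to double uptake, so it creates a group of extra patients whose second scans fall due 12 months on. With 9-month phases, that is inside the enhanced phase. If a patient scanned last year is more likely to be scanned than one who was not, the series rises there even if the enhancement does nothing.

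Nothing planned would separate the two causes. The exclusion does not reach patients first screened after launch. The confounding check names age, gender and race. The COVID-19 propensity step concerns patient characteristics, and prior LDCT is not named. Autocorrelation is tested up to order six, whereas an annual repeat acts at lag 12.

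At stake is whether the enhanced version adds to the first release, the 12.8% to 20% step in the power paragraph.

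**Working it through.** **Inputs from the plan.** Phases of 12, 9 and 9 months; rates of 6.4%, 12.8% and 20%; at least 900 eligible patients a month; two-sided alpha 0.05. **Assumed:** the probability r that a patient screened a year ago is screened again. It is not in the documents, so a range is shown.

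**1. The plan's own figure.** One month of 900 against another gives power 0.996 (6.4% v 12.8%) and 0.985 (12.8% v 20%). A simulated 30-month segmented regression gives about 1.00 for each level change. The stated power of more than 95% is met. The power method the plan cites was not available, so the match is to the inequality only.

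**2. Timing.** Launch is study month 13, so first repeats fall due in month 13 + 12 = 25. The enhanced phase starts in month 12 + 9 + 1 = 22, so month 25 is enhanced month 4. Months 25 to 30 (enhanced months 4 to 9) look back to months 13 to 18, all after launch.

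**3. Size under a calendar-month count with re-entry.** Each patient is counted once a year, the share screened in the year before launch is 6.4%, and the enhancement has no effect. Let s(t) be the proportion screened and a the post-launch rate among patients not screened a year earlier:

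s(t) = r·s(t−12) + a·[1 − s(t−12)]

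Setting s(t) = 0.128 when s(t−12) = 0.064 gives a = (0.128 − 0.064r)/0.936. When s(t−12) becomes 0.128, the series rises by (r − a) × 6.4 points. The phase mean is that rise × 6/9. The planned increment is 20 − 12.8 = 7.2 points.

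| r | a | Rise, enhanced months 4–9 | Series reads | Phase mean | Share of 7.2 |
|---|---|---|---|---|---|
| 0.3 | 11.6% | 1.2 points | 14.0% | 0.8 points | 11% |
| 0.5 | 10.3% | 2.5 points | 15.3% | 1.7 points | 24% |
| 0.8 | 8.2% | 4.6 points | 17.4% | 3.1 points | 43% |

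**4. Where the model puts it.** With a level and a trend change at each break, the enhanced segment is fitted as its own line over nine months. A step of e in the last six has least-squares slope e × 9/60 = 0.15e, and the line starts at e × 6/9 − 4 × 0.15e = 0.067e. The false trend change is therefore 0.18, 0.38 or 0.69 points per month. The false level change is only 0.08, 0.17 or 0.31 points.

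**5. False significance.** This used 20,000 binomial series per r, 30 months at 900 a month, and the six-parameter least-squares fit.

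| r | Trend change significant | Level change significant |
|---|---|---|
| No repeat effect | 7.7% | 7.8% |
| 0.3 | about 17% | about 7% |
| 0.5 | about 45% | about 6% |
| 0.8 | about 82% | about 4% |

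At r = 0.2 the rise is 0.5 points and the trend is significant in about 9% of series. The comparator is 7.7% and not 5%, because least squares pools a variance that differs between segments.

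**6. Other counting rules.** On a rolling 12-month count, the launch effect ramps up over months 13 to 24. A simpler model (repeats equal to 0.3 to 0.9 of the 6.4-point launch excess) then gives a level change of +0.35 to +0.05 points and a trend change of −0.31 to −0.04 points per month. If each patient is counted once, at entry, there is no distortion.

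**7. First-scan series.** In the model of step 3, the first-scan rate is constant at a from month 13, so both enhancement coefficients average zero. In simulation the false trend also disappeared when depletion of the most willing patients was allowed for.

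**The case against.** A reader might infer that the plan does count repeats and so credits the enhancement with them. The documents do not support that: they leave the window and re-entry open, and the only rate with a stated window, the 6.4%, is a 12-month look-back. On a rolling count the false trend is negative. The upward bias is therefore conditional.

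A reader might also infer that the 9-and-9-month schedule guarantees the overlap. The phase lengths are anticipated, the release is approximate, lockdown visits may be removed, and repeats need not fall at exactly 12 months.

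The size can be overstated too. Setting the rise in months 4 to 9 alone against 7.2 points gives 16%, 35% or 64%, but the planned gain is for the whole phase, so 11%, 24% or 43% is the fair comparison. The Inclusion Criteria also widen eligibility between phases 1 and 2, and the Background puts the increase in eligible patients at 67%. If phase 2 is the enhanced phase, which is not stated, the launch cohort's share falls to 1/1.67 = 0.6, and false trend significance falls to about 11%, 23% or 49%.

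The plan would explore nonlinearity if linearity fails. That might reveal a bend, but not its cause.

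Finally, repeats are a legitimate part of the outcome. The payment rule that "required a SDM consultation involving use of a decision aid for payment of initial LDCT screening" is a payer's rule, not the scope of this intervention. The stated purpose is more appropriate screening, and the EHR and portal reminders are for eligible patients, not only never-screened ones. It does not follow that overall uptake is the wrong primary outcome.

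All of this stands. What remains is that the enhancement estimate depends on a counting choice the plan has not made, and that the pooled series cannot separate repeats from an enhancement effect.

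**Conclusion.** The point holds in conditional form. The enhancement trend change is open to upward bias if scans are counted by calendar month, patients can re-enter, and the phases run about as anticipated. For an assumed repeat probability of 0.3 to 0.8, with constant eligibility, the false gain averages 0.8 to 3.1 points over the enhanced phase. At 0.2 it is minor. The level change is not inflated, and launch versus baseline in months 13 to 21 is unaffected. The defect is an incomplete outcome definition and a missing companion series, not a wrong primary outcome. It is worth correcting because the correction is cheap.

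**What to change.** - Keep overall LDCT uptake as the primary outcome, but state the window over which a scan counts and whether, and when, a patient can re-enter.
- Pre-specify the same segmented regression on first LDCT among eligible patients with no prior LDCT on record. Require this series to support any conclusion that the enhancement added to the first release.
- Report repeat LDCT among previously screened patients who are due (last LDCT at least 12 months ago) as a separate series. It would also show any real effect of the enhancement on repeats.

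Cost: SAP wording and one further field, the date of last LDCT, from the data warehouse already in use. The first-scan series will have somewhat fewer patients a month, scans done elsewhere will be missed, and the never-screened pool will gradually lose its most willing members, which pulls modestly against the enhancement.
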